Principal Investigator St. Pierre Hospital	
[name] [contact] Department of Infectious Diseases. St Pierre University Hospital [name]

Principal Investigator UZ Gent	
[name] [contact] [name]

Principal Investigator CHU Liège	
[name] [contact] [name]

TRIAL SUMMARY

Trial Title	Does screening for gonorrhea and chlamydia affect the incidence of these infections in men who have sex with men taking HIV pre exposure prophylaxis (PrEP): a randomized, multicentre controlled trial
Short title	GonoScreen: Efficacy of screening STIs in MSM
Trial Design	Multicentre, controlled, randomized trial of 3 site (urethra, pharynx and rectum) sampling performed every 3 months (3x3) for Neisseria gonorrhoea (Ng)/ Chlamydia trachomatis (Ct) screening (comparator) vs. no screening (intervention)
Trial Participants and setting	PrEP cohorts situated at the Institute of Tropical Medicine (ITM), Hôpital Saint-Pierre (HSP), University Hospital of Gent (UZG), Erasmus Hospital (EH) and Liège University Hospital (CHU). All men in follow up at these five centres who report having had sex with another man in the previous year and are enrolled for PrEP follow up will be eligible to participate in the study.
Intervention	
Participants in the intervention arm will not be screened for Ng/Ct for a period of 12 months, in reference to the routine practice of screening (and treating screening-positive) participants every 3 months.
 
More specifically, participants in the intervention arm will have 3 site (urethra, pharynx and rectum) sampling performed every 3 months but these testing results will only be reported at the end of the 12 month period.

Control	For a period of 12 months, all participants will be screened for Ng/Ct at three sites (urethra, pharynx and rectum) every three months according to current Belgian guidelines. If they test positive, they will be recalled for treatment for Ng/Ct and contact tracing.
Primary Endpoint	Incidence rate of Ng plus Ct detected at any site whilst individuals are screened vs. not screened.
Secondary Endpoint(s)	
 - Cumulative antimicrobial exposure (ceftriaxone/azithromycin/doxycycline) - Incidence of symptomatic Ng plus Ct - Incidence of syphilis - Incidence of HIV - Cost effectiveness of 3x3 screening vs. no screening - Variations in PrEP users' perceptions towards STI screening (only for ITM subjects)
Planned Sample Size	1014 participants
Intervention duration	12 months
Follow up duration	Not applicable
Duration of the trial (FPI-CSR)	2 years and 2 months (26 months)

FUNDING AND SUPPORT IN KIND

There are no other commercial organisations/entities involved in this study besides the KCE as a funder.

ROLE OF STUDY SPONSOR AND FUNDER

The Institute of Tropical Medicine as mentioned in KEY TRIAL CONTACT shall act as sponsor of the Study, as defined in the Law of 2004, and shall assume all responsibilities and liabilities in connection therewith and procure the mandatory liability insurance coverage in accordance with the Law of 2004. **The Institute of Tropical Medicine** shall ensure that it shall be mentioned in the Protocol, the Informed Consent Forms and in other relevant communication with the Study Subjects or the Regulatory Authorities as sponsor of the Study. **The Institute of Tropical Medicine** acknowledges and agrees for the avoidance of doubt that KCE shall under no circumstances be considered as sponsor of the Study or assume any responsibilities or liabilities in connection therewith, and **The Institute of Tropical Medicine** shall make no representations whatsoever in this respect.

ROLES AND RESPONSIBILITIES OF TRIAL MANAGEMENT COMMITTEES

The GonoScreen Trial organogram is depicted in Figure 1.

1) Trial Steering Committee (TSC)

The Trial Steering Committee (TSC) will be responsible for the overall supervision and safety monitoring of the trial. The TSC will be constituted by the Principal Investigators (PIs) of the five study sites, the study statistician and a member of the ITMs Clinical Trials Unit (CTU). It will also include a representative from the participant community and a representative from the KCE who is independent of the investigators, their employing organisations and sponsors. The TSC will monitor trial progress, and give advice on the scientific implementation of the trial and its continuation. The TSC is also responsible for the development of a study publication plan. The TSC will meet at least 3 times per year during the first year and two times a year after that. A meeting report will be written after every TSC meeting and will be distributed to all members of the TSC and TMG.

2) Trial Management Group (TMG)

[figure not shown]
The day-to-day management of the study will be performed by the Trial Management Group (TMG) which is distinct from the TSC. The TMG will consist of the same members as the TSC, except the representative from the participant community and the KCE representative will not be members. The following will be members: STI laboratory managers from ITM, HSP, EH, UZG and CHU and the head of the social science work package from ITM. The TMG will meet once a month on average during the whole duration of the trial and will be responsible for the daily management of the trial and site-specific questions/issues. After every TMG meeting, a report will be written including pending actions assigned to specific parties which will be distributed to all partners in the project.

3) Data and Safety Monitoring Board (DSMB)

We will set up an independent Data and Safety Monitoring Board (DSMB) to evaluate if the non-screening arm has an unacceptably high incidence of symptomatic Ng/Ct. Two independent STI experts (Infectious Disease Physicians/Epidemiologists) will constitute the DSMB and will be joined by the sponsor study statistician for the DSMB meetings.

The DSMB will evaluate the incidence of symptomatic Ng + Ct in both arms once 50% and 100% of individuals have completed their 6 month visit. If the incidence of symptomatic Ng + Ct in the non-screening arm is more than two-fold higher than the screening arm at either of these time points, then serious consideration should be given to stopping the study (further details in Section 10 and Appendix 1).

Figure 1. GonoScreen Trial Organogram

[figure not shown]
LIST OF ABBREVIATIONS

ABBREVIATION	DEFINITION
AE	Adverse Event
AIDS	Acquired Immune Deficiency Syndrome
AMR	Anti-Microbial Resistance
APR	Annual progress report
ARC	AIDS Reference Centre
BCFI	Belgian Centre for Pharmacotherapeutic Information
BREACH	Belgian Research on AIDS and HIV Consortium
CHU	Liège University Hospital
CI	Coordinating Investigator
CRF	Case Report Form
Ct	Chlamydia trachomatis
CTU	Clinical Trials Unit
DSMB	Data and Safety Monitoring Board
EC	Ethics Committee
ECDC	European Centre for Disease Prevention and Control
EH	Erasmus Hospital
EU	European Union
FAMHP	Federal Agency for Medicines and Health Products
FGD	Focus Group Discussion
FU	Follow Up
GCP	Good Clinical Practice
GCLP	Good clinical laboratory practice
GDPR	General Data Protection Regulation
GP	General practitioner
HIV	Human Immunodeficiency Virus
HSP	Hôpital Saint-Pierre
ICF	Informed Consent Form
ICH	International Conference on Harmonisation of technical requirements for registration of pharmaceuticals for human use.
IF	Investigator File
IMP	Investigational Medicinal Product
IRB	Institutional Review Board
ISF	Investigator Site File
ITM	Institute of Tropical Medicine
IUSTI	International Union against Sexually Transmitted Infections
KCE	Belgian Healthcare Knowledge Centre
LHUB	Laboratoire Hospitalier Universitaire de Bruxelles
MSM	Men who have Sex with Men
NAAT	Nucleic acid amplification testing
Ng	Neisseria gonorrhoea
PI	Principal Investigator
PIS	Participant Information Sheet

PrEP	Pre-Exposure Prophylaxis
QA	Quality Assurance
QoL	Quality of life
RCT	Randomised Control Trial
RIZIV/INAMI	Rijksinstituut voor ziekte- en invaliditeitsverzekering/ Institut national d'assurance maladie-invalidité
SAP	Statistical analysis plan
SDV	Source Data Verification
SIV	Site initiation visit
SOP	Standard Operating Procedure
STI	Sexually Transmitted Infection
TDF/FTC	Tenofovir disoproxil fumarate/Emtricitabine
TMG	Trial Management Group
TSC	Trial Steering Committee
TMF	Trial Master File
USA/U.S.	United States of America
USV	Unscheduled Visit
UZA	University Hospital of Antwerp
UZG	University Hospital of Gent
WHO	World Health Organization
3x3 screening	Screening 3-sites -pharynx, rectal and urethral- at 3 monthly intervals

TRIAL FLOW CHART

Figure 2. Trial flowchart

■ STUDY PROTOCOL

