3 ASSESSMENT AND MANAGEMENT OF RISK

We acknowledge the ethical concern that the study may result in an increase in symptomatic disease in individuals (and their partners) in the no-screening arm. We justify this possible increased risk by an appraisal of the available evidence which reveals that we have no high-quality evidence that the 3-monthly, 3-site Ng/Ct screening in MSM PrEP cohorts (3x3 screening) is beneficial. We do have evidence that 3x3 screening likely results in harm [6, 16]:

1. **Adverse effects of antibiotics** as noted above[15, 36-39].
2. **Arrested immunity** as noted above [29, 30]. If screening results in 'arrested immunity' it may thus paradoxically increase Ng/Ct prevalence/symptomatic disease.
3. **Certificate of health effect.** A number of studies have argued that screening may result in a "certificate of health" effect whereby those screened may feel that if they come for regular screening this gives them a bill of health that means they can relax safety devices perceived to be onerous such as condom use [16, 40].

Our risk assessment concludes that based on the available evidence stopping screening may be associated with either an increase or a decrease (given arrested immunity) in symptomatic Ng/Ct infections and Ng/Ct spread. Stopping screening will almost certainly be associated with a lower antimicrobial exposure and lower costs.

To minimize the risks, the study is planned to be conducted in a limited and closely-monitored cohort of MSM, already attending scheduled visits at the 5 HIV PrEP clinics. As such, participants will continue to receive appropriate counselling related to practicing safe sex. Participants in the intervention arm will be followed-up with the same intensity and frequency as participants in the comparator arm. In both arms, symptomatic infections, including contact tracing, will be treated throughout the study period and according to standard of care. The safety monitoring board will evaluate if there is an increase in the incidence of symptomatic Ng/Ct infections at the 6 month visits in the non-screening arm. If this would exceed a pre-specified threshold, the study will be stopped (See Section 10).

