10.2 Responsibilities

Principal Investigator (PI):

The PIs and delegated study doctors at each study site will be responsible for ensuring that all episodes of symptomatic Ng/Ct infections are adequately investigated, treated, followed up and reported so as to allow a timely assessment of any excess incidence of symptomatic Ng/Ct in the non-screening arm.

They will also be responsible for correct documentation of these STIs in the source documents and in the corresponding eCRFs.

Sponsor:

1. The sponsor will be responsible for the central data collection of these STIs through the eCRF database.
2. The sponsor will be responsible for informing the Trial Steering Committee (in particular the two independent experts) at 6 and 9 months of the amount of STIs that have occurred since the start of the study.

TSC:

The TSC (two independent STI experts in particular) will be responsible for evaluating the STI incidence at regular intervals and advising the sponsor on continuation of the trial.

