11.2 Planned recruitment rate

The 5 centres will begin recruitment at the same time and will continue recruiting all PrEP participants until the recruitment target is reached (estimated 8-month recruitment period). The planned recruitment rate will be 127 individuals per month for this 8-month period. To the best of our knowledge, there are no other trials being conducted currently or planned that are evaluating the same research question or a version thereof.

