Interim analyses are planned at two time points: once 50% and 100% of all study recruits have passed their 6 month visit. For the first interim analysis, data is used of the first 507 enrolled participants (i.e. ordered by randomization date) until 6 months follow-up. For the second analysis, data is used of all enrolled participants until 6 months follow-up. The goal of the interim analyses (at both time points) is to estimate the incidence rate ratio of symptomatic Ng plus CT. Estimates will be based on a Poisson regression model (or a negative binomial regression model if there is overdispersion) with number of symptomatic diagnoses as dependent variable, arm and hospital as independent variables and log(number of visits) as offset. This model will provide estimates of the incidence rate in each arm and the incidence rate ratio (no screening versus screening), together with 95% confidence interval. Visits with missing data on the diagnosis of Ng or Ct, will be excluded from the calculation of the incidence rate (excluded both from numerator and denominator).

7. Analysis of main efficacy outcomes: Incidence of Ng plus Ct

In each arm, the incidence of Ng plus Ct will be estimated together with 95% confidence interval. Estimates will be based on a Poisson regression model (or a negative binomial regression model if there is overdispersion) with number of diagnoses as dependent variable, arm and hospital as independent variables, and log(number of visits) as offset. This model will also provide an estimate of the log incidence rate ratio (no screening versus screening), together with 95% confidence interval. The 'no screening' arm is proven to be non-inferior if the upper limit of the 95% confidence interval is lower than $\log(1.25)$.

Visits with missing data on the diagnosis of Ng or Ct, will be excluded from the calculation of the incidence rate (excluded both from numerator and denominator).

In a sensitivity analysis, the numerator of the primary endpoint will only include diagnoses if there was a negative test result at the prior visit.

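### The second DSMB look falls at about month 14, when roughly one eighth of the withheld results are still ahead; using all accrued data, the same number of visits is available by about month 11.5

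*Protocol*

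**What the plan says.** The DSMB paragraph of the protocol's roles section, repeated in Appendix 1, has incidence evaluated "in both arms once 50% and 100% of individuals have completed their 6 month visit". Section 10.1.1 gives the same two time points but speaks of participants having *passed* the visit. SAP section 6 also says *passed* and fixes the data: for look 1, "data is used of the first 507 enrolled participants (i.e. ordered by randomization date) until 6 months follow-up"; for look 2, "For the second analysis, data is used of all enrolled participants until 6 months follow-up".

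On accrual, protocol section 11.2 states: "The planned recruitment rate will be 127 individuals per month for this 8-month period". Section 8.7 allows the month 6 visit from one week early to six weeks late. It also says that no-screening participants are not told their month 3, 6 and 9 results, but do receive those of months 0 and 12.

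Section 3 lists DSMB monitoring among the steps taken to limit risk: "The safety monitoring board will evaluate if there is an increase in the incidence of symptomatic Ng/Ct infections at the 6 month visits". Section 10.2 gives another timetable, in which the sponsor must inform the steering committee, chiefly its two outside STI specialists, "at 6 and 9 months of the amount of STIs that have occurred since the start of the study".

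**The concern.** A look protects participants only to the extent that exposure is still ahead when it happens. The documents tie both looks to month 6 visits but never convert this to calendar time, and do not discuss how much of the unscreened period would remain. If most of it has passed by look 2, a finding of excess symptomatic infection could change little for those taking part. The cut at 6 months and the limit to the first 507 would also mean that the DSMB waits for data while comparable data already collected are set aside. Section 10.2 adds a timetable that does not match, so it is unclear who sees what, and when.

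**Working it through.** **Inputs.** N = 1,014 and 10% dropout (protocol 11.1); 127 per month for 8 months (11.2); visits at months 3, 6, 9 and 12, with results of months 3, 6 and 9 withheld (8.7); look definitions (SAP 6). Assumed: uniform entry, visits on time, no data-cleaning lag and, at first, full retention.

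**The plan's own figures.** 1,014/8 = 126.75, stated as 127. 912/0.9 = 1,013.3, rounded up to 1,014. Both reproduce.

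**Calendar time of the looks.** Participant 507 enters at month 4 and the last at month 8.
- Look 1: 4 + 6 = month 10, two months after enrolment closes. With accrual over A months, look 1 precedes closure only if A/2 + 6 < A, that is A > 12.
- Look 2: 8 + 6 = month 14, or about 15.4 to 15.5 if the last month 6 visit is six weeks late.

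**Follow-up elapsed.**
- Month 10: mean time since entry is 10 − 4 = 6 of 12 months, or 50%.
- Month 14: (2 × 12 + 6 × 9)/8 = 9.75 of 12 months, or 81%.
- Month 15.5: (3.5 × 12 + 4.5 × 9.75)/8 = 10.73 of 12 months, or 89%. Simulation with random visit timing inside the window reaches 90%.

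**Withheld results still ahead.** The share of participants past visit m at time T is (T − m)/8, held between 0 and 1. Averaging the remainder over m = 3, 6, 9:
- Month 10: (1/8 + 4/8 + 7/8)/3 = 50%; 34% if the look is six weeks late.
- Month 14: (0 + 0 + 3/8)/3 = 12.5%; 6.7% if only the look is six weeks late; 8% to 12% with random windows.
- Month 11.5: (0 + 2.5/8 + 5.5/8)/3 = 33%.

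**Visits available.** Summing the shares past each visit and multiplying by 1,014:

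| Data set | Month | Visits | After month 3 | Withheld results ahead |
|---|---|---|---|---|
| Look 1 as planned | 10 | 1,014 | 507 | 50% |
| All data | 10 | 1,521 | 634 | 50% |
| Look 2 as planned | 14 | 2,028 | 1,014 | 12.5% |
| All data | 11.5 | 2,028 | 1,014 | 33% |
| All data | 14 | 2,915 | 1,901 | 12.5% |

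For month 11.5 the shares are 1 + 5.5/8 + 2.5/8 = 2.0, of which 1.0 is after month 3. The plan leaves 1,521 − 1,014 = 507 visits unused at month 10 and 2,915 − 2,028 = 887 at month 14.

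**Why visits after month 3 are counted separately.** Positive baseline tests are treated in both arms (8.1.2) and the first withheld result is that of month 3, so the arms are managed alike until then. Suppose the true ratio is 1 up to month 3 and 2 afterwards, with equal screening-arm rates per visit. The pooled ratio is then 1 plus the share of visits after month 3: 1.50 at either planned look and at month 11.5 with all data, but 1 + 634/1,521 = 1.42 at month 10 with all data. An offset corrects for the amount of exposure, not for this dilution.

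**Dropout check.** If all of the 10% dropout came before month 6, the 1,014 post-month-3 visits would be reached when (T − 6)/8 + (T − 9)/8 = 1/0.9, so T = 11.9. Among those retained, (2.06/8 + 5.06/8)/3 = 30% of withheld results would still be ahead.

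**The case against.** A reader might infer that both looks are too late to be of use. The figures do not support that: at look 1 half of follow-up and of withheld results remain. Nor is look 2 empty. At month 14, the 75% who entered after month 2 are still in follow-up, with 3 months left on average, and 37.5% have not reached month 9.

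A reader might also infer that look 1 should move to the close of enrolment. At month 8 it would still prevent no enrolment. It would hold 1,014 × 2/8 = 254 post-month-3 visits against 507 planned, out of 1,014 × (5/8 + 2/8) = 887, so the pooled ratio above would fall to 1.29. For look 1, then, waiting does buy information, and a month 6 trigger is a defensible way to secure a full unscreened interval.

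Section 3 relies on more than the DSMB: a closely monitored cohort, counselling, equal follow-up, and treatment of symptomatic infections with contact tracing in both arms. Withheld results are therefore a proxy for avoidable exposure, not a count of harm. Section 10.1.1 calls the schedule a proposal and leaves threshold and method to the DSMB. If the 6 and 9 months in section 10.2 are calendar time, the first report comes with 25% still to enrol. However, that section describes an amount of STIs, with no comparison by arm and no rule, so it does not replace a look.

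None of this touches look 2, where the same number of visits, with the same split around month 3, exists about 2.5 months sooner.

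**Conclusion.** The point holds for look 2 and for the data restriction in SAP section 6; it does not hold as a claim that monitoring as a whole comes too late. The no-screening arm has 507 participants and 3 × 507 = 1,521 withheld results. At month 14 about 190 of these (12.5%) are still ahead, against about 507 (33%) at month 11.5.

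One eighth is the on-schedule value, not a strict bound. It is about 14% if the look is a week early, and (4.38/8)/3 = 18% if month 9 visits all run six weeks late while the last month 6 visit is on time. A late last visit or a data-cleaning lag lowers it. With uniform accrual over A months the share is (3/A)/3 = 1/A: 17% for 6 months, 10% for 10 and 8% for 12. Slower accrual therefore makes look 2 less useful.

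The match at month 11.5 is in the number of visits and the split around month 3. It is not identical by visit: about 697 month 6 and 317 month 9 visits stand in for 1,014 month 6 visits.

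The *completed* wording is a smaller matter. Read literally, 100% cannot be reached if any of the planned dropout precedes month 6; section 10.1.1 and SAP section 6 avoid this with *passed*.

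**What to change.** - **SAP section 6:** at each look, use all follow-up accrued on everyone enrolled, and show results separately for visits up to month 3 and after month 3.
- **Look 2** (protocol DSMB paragraph, section 10.1.1, Appendix 1, SAP section 6): trigger it when 1,014 scheduled visits after month 3 have accrued, at about month 11.5. Keep the look when all have passed month 6 as a further report.
- **Look 1:** leave it at about its planned time, with all accrued data: 634 post-month-3 visits at month 10 against 507 planned.
- **Section 10.2:** state whether 6 and 9 months means calendar or participant time, what is reported and whether by arm, and reconcile it with the DSMB schedule.
- **Wording:** use *passed* rather than *completed* throughout.

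The cost is protocol and SAP text, one further DSMB report, and unequal follow-up per participant at the looks. No new data are collected. Looks 1 and 2 would be only about 1.5 months apart, with 2,028 − 1,521 = 507 new visits between them, 1,014 − 634 = 380 of these after month 3. The threshold for action is not part of this point and is left to the DSMB.

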1 BACKGROUND

[figure not shown]
Neisseria gonorrhoeae (Ng) is a common sexually transmitted infection whose incidence has been noted to be increasing in key populations such as men who have sex with men (MSM) taking HIV pre exposure prophylaxis (PrEP) in many countries [1, 2]. In part, this increased incidence is an artefact of more intensive screening [3]. Longitudinal studies of MSM PrEP cohorts have typically found a high but stable incidence of Ng and *Chlamydia trachomatis* (Ct) [2]. Infections in MSM can occur at 3 sites – the oropharynx, urethra and anorectum [1, 2]. The vast majority of infections in MSM are asymptomatic and self-limiting [1]. The high incidence of Ng and Ct in MSM PrEP cohorts has prompted calls for frequent screening for these infections [4]. The Belgian PrEP guidelines, for example, currently mandate 3x3 screening (screening 3-sites -pharynx, rectal and urethral- at 3 monthly intervals) for all PrEP recipients [2, 5]. Of note these guidelines were not based on evidence from clinical trials but based on the fact that guidelines from other countries recommend 3x3 screening, even in the absence of scientific data from clinical studies in these countries [2, 5]. Because there is so little evidence to justify screening and screening entails an appreciable cost, there is considerable heterogeneity in the intensity of Ng/Ct screening between PrEP centres within Belgium. In some centres, only one site is tested every 3-6 months. In other centres all three sites are tested every 3 or 6 months.

Possible negative effects of intensive screening

A major concern of this intensive screening is that it will select for antimicrobial resistance (AMR) in Ng and other bacteria. Because the vast majority of Ng and Ct are asymptomatic in MSM, 3x3 screening and subsequent treatment (compared to only treating symptomatic infections) increases antibiotic exposure by up to 60-fold [6] and results in consumption rates of azithromycin and ceftriaxone that have been found to result in high rates of AMR in a range of bacteria in various studies [7-9]. One analysis for example found that 3x3 screening in PrEP cohorts results in macrolide exposures of up to 4400 standard doses/1000 population per year [6]. This exposure level is 41 times greater than that of populations such as Latvia and considerably higher than exposure levels found to be strongly associated with the induction of antimicrobial resistance (AMR) in a range of bacteria [6]. This degree of antimicrobial exposure carries a high risk of producing resistant microbiomes and thereby increasing the risk of infections with resistant bacteria. This includes both non-STIs (Sexually transmitted infection) such as *Staphylococcus aureus* as well as STIs such as Ng and *Treponema pallidum* (Figure 3). We and others have found evidence that populations with higher levels of antimicrobial consumption have higher rates of AMR in Ng [9-11]. Furthermore, we have found historical evidence that the intensive Ng screening and treatment campaign in Greenland in the 1960s was followed by a steep-increase in gonococcal AMR [12]. Finally, we have also found ecological level associations between the intensity of Ng/Ct screening in MSM and gonococcal AMR in both the USA and Europe [13, 14].

Figure 3. An illustration of how frequent screening for *N. gonorrhoeae* in MSM PrEP populations may have little effect on reducing prevalence of *N. gonorrhoeae* but result in the development of antimicrobial resistance.

Period (1) The high sexual network connectivity of a typical PrEP cohort (top) translates into a high equilibrium prevalence of *N. gonorrhoeae* (green squares). Period (2) Active screening of a quarter of this population (black bordered squares) results in a lower *N. gonorrhoeae* prevalence in period 2 but at the expense of an altered resistome (yellow squares represent individuals with *N. gonorrhoeae* cleared via antibiotics in preceding period). Because the network connectivity remains unchanged, *N. gonorrhoeae* tends to return to its equilibrium prevalence. This places recently cured individuals (such as individual "a") at high risk of reinfection at a time when their resistomes are enriched with resistance genes (azithromycin for example leads to elevations of resistance genes for up to 4 years [15]). An early *N. gonorrhoeae* reinfection in "a" is able to take up these resistance genes via transformation and become resistant to the antibiotics used to treat *N. gonorrhoeae* (red squares). Period (3) If there is ongoing high exposure to antibiotics these less susceptible *N. gonorrhoeae* strains will have a fitness advantage over more susceptible strains. These dynamics would be predicted to favor the emergence and spread of resistant *N. gonorrhoeae*. By period 3, *N. gonorrhoeae* has returned to its equilibrium prevalence for this degree of network connectivity but now most strains are resistant. The degree of connectivity in the low connectivity population (bottom) is so low that *N. gonorrhoeae* remains at a very low prevalence. Even extensive screening is unlikely to result in sufficient antibiotic exposure to provide *N. gonorrhoeae* access to resistance genes or a fitness advantage for resistance strains (Uninfected individuals: gray squares; Edges between squares represent sexual relationships) (Figure from [16]).

Preventing the emergence of untreatable gonorrhoea

N. gonorrhoeae (Ng) has developed AMR to every single antibiotic used against it [17, 18]. This plus recent reports of combined high level resistance to ceftriaxone and azithromycin have led to concerns it will be untreatable in the near future [17, 18]. The World Health Organization and others classify Ng as being at high risk for further development of AMR and one of the strategies advocated to reduce

the probability of further AMR developing is antimicrobial stewardship [19, 20]. This involves reducing the use of antimicrobials to clearly defined indications where benefit clearly outweighs risk [20, 21]. Gonococcal AMR has typically emerged in core groups such as MSM PrEP cohorts that have high rates of partner change and high levels of antimicrobial consumption [22, 23]. These considerations mean that it is critical to ensure that antimicrobial consumption in MSM PrEP cohorts is limited to indications where there is clear evidence of benefit [6, 16].

Which STIs should be screened for in MSM?

According to the World Health Organization and others, screening programs should only be introduced if they fulfill various criteria [24]. Two of these criteria are that there should be scientific evidence of screening effectiveness and that the overall benefits of screening should outweigh the harms [24].

The increasing concerns about AMR and reducing excessive antibiotic consumption in MSM have led us and others to re-evaluate the available evidence as to the benefits and harms of screening for each STI in MSM [4, 16, 22]. We concluded that whilst the evidence in favour of screening was strong for HIV, syphilis and hepatitis C, it was weak and contradictory for Ng and Ct [16]. These conclusions were based on the following types of evidence:

- **No Randomised Control Trial (RCT) have ever been conducted** or are planned in MSM or other men to evaluate the benefit/risk of Ng/Ct screening [5]. As a result, the U.S. Preventive Services Task Force guideline concludes that there is insufficient evidence to make a recommendation as to whether or not screening for these infections should be conducted in men [5].
- A **systematic review of observational studies** in MSM found that screening was not associated with reductions in prevalence of Ng or Ct [6]. Evidence from the ITM's PrEP cohort, for example, demonstrates that the prevalence of Ng and Ct remain about 10% each despite 3 monthly screening/treatment [7].
- We have evaluated if there was an **ecological association between screening intensity and Ng prevalence** in MSM. There are wide variations in the intensity of self-reported Ng/Ct screening in MSM both between countries within Europe and within States in the United States of America. In neither of these examples is there a *negative* association between screening intensity and Ct or Ng prevalence in MSM. For example, in Europe we compared self-reported national STI screening rates from a behavioural survey of 180 000 MSM from across Europe (European MSM Internet Survey) with European Centres for Disease Prevention and Control national estimates of Ng and Ct incidence from the same year 2010 [25]. We found *positive* association between these variables for both Ng and Ct (Rho =0.74; P=0.0004 and Rho=0.71; P=0.001, respectively). This positive association may be due to the fact that more intense Ng/Ct screening would be expected to generate higher incidence estimates. To avoid this bias, we used incidence estimates generated from more comparable studies of Ng/Ct prevalence estimates from MSM attending STI clinics. We found no evidence of an association between screening intensity and Ng incidence [25]. The results from the USA were similar (Unpublished data).
- **Modelling studies** have reached somewhat different conclusions as to the efficacy of Ng/Ct screening [8]. One study found that screening may lead to meaningful reductions in Ng prevalence [26]. A modelling study by our group that, unlike the prior study, included

pharyngeal transmission found screening to have a minimal effect on Ng prevalence in Belgian MSM but a large effect on antimicrobial exposure [3].

- ***The biology of Ng and Ct host interactions make them less amenable to screening than HIV, syphilis and hepatitis C*** [16]. In the case of Ng, numerous aspects of the way it circulates in MSM decrease the probability that screening will be beneficial. Symptomatic disease is thought to typically occur soon (2–21 days) after infection. If symptoms do not develop, the infection (particularly in the pharynx and rectum) tends to persist in a low abundance state for one to 6 months [27]. Highly exposed individuals develop a type-specific immunity but this immunity is largely ineffective in low exposure individuals [27, 28]. The vast majority of Ng infections are asymptomatic and self-limiting in this population [27, 28]. Screening is far more likely to diagnose infections in the 6 month asymptomatic tail phase (when Ng abundance is likely lower and therefore less infectious) than in the acute first weeks post infection. These features reduce the probability that screening will decrease either symptomatic infections or Ng transmissions—assuming that the low abundance infections are less infectious. Similar considerations apply to Ct. In the case of *C. trachomatis* there is however better evidence that treatment of Ct results in “arrested immunity” and thereby paradoxically increases the probability of reinfection and may even lead to increases in prevalence [29, 30].
- ***High risk of inducing AMR.*** As noted above, gonorrhea/chlamydia screening in MSM can result in exposure levels to macrolides/cephalosporins that are strongly associated with resistance in Ng, *Treponema pallidum* and a range of other bacteria [8-10].

The fact that we have no clear evidence of 3x3 Ng/Ct screening being beneficial in this population combined with the fact that this policy results in such high rates of antimicrobial consumption in this population mean that randomized controlled trials are urgently required to assess the utility of 3x3 screening [16].

